8.1.2.3 Very severe RSV LRTI

A very severe RSV LRTI case is defined as:

- RSV LRTI hospitalization
- oxygen saturation < 90% (at any time during hospitalization)
- oxygen supplementation

With the addition of oxygen saturation < 90% and oxygen supplementation, very severe RSV LRTI cases are to be identified, described, and documented in the same way as RSV LRTI hospitalization (Section 8.1.2.2).

8.1.2.4 Wheeze

During the 12- and 24-month follow-up call, the site investigator or staff designee will ask to parents/LARs of UK reconsented participants if the participants had experienced any medically attended cough, chest or breathing problems throughout the study period.

After the 12-month follow-up phone call (when possible) and the 24-month follow-up phone call, the site investigator or staff designee (including third parties authorized by the site investigators) will access the UK reconsented participants' medical record (general practitioner's or hospital's record) to determine if the medical event meets with the definition of wheeze provided by the Sponsor (see below). If so, the event and related complementary information (including any medications prescribed during wheeze) will be retrospectively collected.

For this study, wheeze will be defined as a physician-diagnosed wheeze or asthma or related ear, nose and throat (ENT)/respiratory symptoms at an office visit or an illness for which the child was prescribed medication to treat an ENT/respiratory condition.

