In order to minimize the burden on sites, families and participants, while still answering the objective of this protocol amendment, it was decided to invite in the study extension only the UK participants, who represent 50% of the study population.

Enrollment of Study Participants

A total of 28 860 participants will be enrolled from sites in France, Germany, and the United Kingdom. The study will enroll infants born either out of the RSV season or in the RSV season.

Definition of the RSV season

There is an important variability of RSV seasonality from year to year in each country. The typical RSV season in the Northern Hemisphere (NH) last approximately 5 months and usually starts in October or November. Therefore, the "Out-of-Season" period refers to the approximately 7 months period from March or April to September or October. The actual start date and length of the RSV season will depend on the actual circulation of RSV in the NH in 2022.

Cases of LRTI hospitalization will be collected throughout the study to ensure that all cases occurring during the next RSV season are captured. For the need of this study, the start and end dates of the RSV season will be defined on a country-by-country basis and will be based on country-specific epidemiological surveillance. For the mothers of infants to be born in-season, recruitment will start at 30 weeks gestation in women with an estimated delivery date during the RSV season.

Rationale for the Collection of Safety Data

Immediate AEs

As nirsevimab is not a marketed product, a 30 minutes immediate surveillance period of infants enrolled in the nirsevimab group will be done on the site where immunization was performed.

Non-serious AEs

For a period of 30 days post-dosing/randomization, non-serious AEs will be captured in the eCRF for all study participants. The relation of AEs to interventional product will be determined by the Investigator.

The use of the eDiary by parents and the process for reporting AEs in the eCRF is outlined in Section 8.2.3.

Hospitalizations

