9.1 Statistical Hypotheses

The primary and key secondary efficacy objectives will be assessed in the Primary Analysis (see Section 9.4 for details of the Primary Analysis) by a hierarchical order. Details on statistical methods are provided in Section 9.4.

For the primary objective, a superiority approach will be used to assess the efficacy of nirsevimab in preventing RSV LRTI hospitalization through the RSV season compared to no intervention in all 3 countries combined. Only if the superiority for the primary endpoint is demonstrated, a superiority approach will be used to assess the efficacy of nirsevimab in preventing very severe RSV LRTI through the RSV season compared to no intervention in all 3 countries combined, and no multiplicity adjustment is needed for this.

If the superiority for very severe RSV LRTI through the RSV season is demonstrated, a superiority approach will be used to assess the efficacy of nirsevimab in preventing RSV LRTI hospitalization through RSV season compared to no intervention in each country separately. For this, Bonferroni adjustment of 2-sided α (ie, 0.05/3) is used to correct multiple testing in 3 countries in the sample size calculation and Bonferroni-Holm procedure will be used in the statistical analysis. For other secondary objectives and observational objectives, no hypotheses will be tested and the analyses will be descriptive.

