9.4.3.3 Other secondary efficacy endpoints

Efficacy and its 95% CIs for nirsevimab in reducing the following efficacy endpoints as compared to the control will be calculated using the exact method as described in the primary efficacy analysis for the exploratory purpose:

- Overall hospitalization for all-cause LRTI in all 3 countries combined throughout the RSV season
- RSV LRTI hospitalization through 150 days post-dosing/randomization (overall and in each country)
- Very severe RSV LRTI in all 3 countries combined through 150 days postdosing/randomization
- Overall hospitalization for all-cause LRTI in all 3 countries combined through 150 days post-dosing/randomization
- RSV LRTI hospitalization through 180 days post-dosing/randomization (overall and in each country)
- Overall hospitalization for all-cause LRTI in all 3 countries combined through 180 days post-dosing/randomization
- Recurrent wheeze throughout the study period in UK reconsented participants

Analyses for the above efficacy endpoints through 150 days post-dosing/randomization and through 180 days post-dosing/randomization will be performed only at the First Year Analysis after all data are collected. Details of the analyses and additional analyses if deemed necessary will be described in the SAP.

Descriptive analyses of the incidence of RSV LRTI hospitalization and all-cause LRTI hospitalization and the incidence of recurrent wheeze with its 95% CIs for nirsevimab and the no intervention will be presented in UK reconsented participants.

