6.6.4.3.7. Recurrent Wheeze Events in UK Reconsented Participants

Recurrent wheeze event is defined as two or more protocol-defined wheeze episodes throughout follow-up period. For the participants who have recurrent wheeze events, the end date will be the date of the second protocol-defined wheeze episode.

At the time of Second Year Analysis, incidence of recurrent wheeze events in UK reconsented participants will be summarized by the treatment group. Descriptive statistics will be provided only. Analyses will be performed at the following timepoints:

- Through Day 366 post-dosing/randomization

For participants without medical records retrospectively reviewed after 24 months, the end date will be the start date (date of randomization for participants randomized to no intervention / date of immunization for participants randomized to nirsevimab and treated / date of randomization for participants randomized to nirsevimab but not treated).

For participants with medical records retrospectively reviewed after 24 months and confirmation of no recurrent wheeze events, the end date will be Day 366 or last available date with confirmation of no recurrent wheeze events, whichever is earlier.

Notes:

- If second or subsequent wheeze event occurs after Day 366, it will not be considered and then the end date will be Day 366.
- If a participant receives Beyfortus as part of a routine immunization, any wheeze event occurring after Beyfortus immunization but before Day 366 will not be considered and the end date will be the date of injection of Beyfortus.

- From Day 366 to Day 731 post-dosing/randomization

For participants without medical records retrospectively reviewed after 24 months, the end date will be the start date (date of randomization for participants randomized to no intervention / date of immunization for participants randomized to nirsevimab and

treated / date of randomization for participants randomized to nirsevimab but not treated).

For participants with medical records retrospectively reviewed after 24 months and confirmation of no recurrent wheeze events, the end date will be Day 731 or last available date with confirmation of no recurrent wheeze events, whichever is earlier.

Notes:

- If wheeze events occur before Day 366 or after Day 731, they will not be considered, only wheeze events occurring between Day 366 and Day 731 will be considered.

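### The wheeze definition does not require wheeze, so reported recurrent wheeze may largely reflect common respiratory illness, and a true difference could be diluted or an apparent one created

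*Protocol*

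**What the plan says.** Protocol 8.1.2.4 has three limbs joined by *or*. The first two are in one clause: "wheeze will be defined as a physician-diagnosed wheeze or asthma or related ear, nose and throat (ENT)/respiratory symptoms at an office visit". The third is "an illness for which the child was prescribed medication to treat an ENT/respiratory condition". Records are searched for qualifying events after parents have been asked "if the participants had experienced any medically attended cough, chest or breathing problems throughout the study period".

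The SAP adopts this definition unchanged: "Recurrent wheeze event is defined as two or more protocol-defined wheeze episodes throughout follow-up period" (SAP 6.6.4.3.7). It applies the rule to three periods: to Day 366, Day 366 to Day 731, and to Day 731. The only sensitivity analysis for this endpoint is triggered when more than 20% of reconsented participants lack a record review. It does not vary the definition, and no breakdown by qualifying criterion is planned.

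The endpoint is secondary but not key. Protocol 9.1 states: "For other secondary objectives and observational objectives, no hypotheses will be tested and the analyses will be descriptive". The SAP section states: "Descriptive statistics will be provided only".

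**The concern.** The objective in Protocol Section 3 is the incidence of recurrent wheeze from D01 to D731. Protocol 2.2 gives the background: later wheeze after severe RSV bronchiolitis in infancy. Protocol 8.1.2.2 treats wheeze as a specific clinical sign, listed beside rhonchi, rales and crackles. The endpoint definition is much wider. Two medicated coughs or colds qualify, and so does one true wheeze plus one cold.

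Two things are at stake. First, the incidence in each arm carries a label that it may not deserve, which matters even for a purely descriptive table. Second, the comparison between arms becomes hard to read. Illnesses that nirsevimab does not affect pull the ratio toward one. Acute RSV illnesses that it does prevent pull it the other way, without any change in later wheeze.

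**Working it through.** **The plan's own figure.** There is none to reproduce: neither document gives a wheeze rate, effect size or precision target. The cohort has an upper bound. Protocol 4.2 restricts the extension to "only the UK participants, who represent 50% of the study population", so 28 860 × 0.50 = 14 430, or at most 7215 per arm before losses at reconsent.

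**Does any limb require wheeze?** The first does. The second may, if *related* refers back to wheeze or asthma. The third has no such tie. The SAP's recurrence rule adds a count and no specificity.

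**Dilution, under assumptions.** Let w be the proportion of controls with true recurrent wheeze, reduced by 30% with nirsevimab. Let q be the proportion with two or more other qualifying illnesses, unaffected by treatment and independent of wheeze. All three are assumptions: w = 15–25%, reduction 30%, q = 50–90%.

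- Cumulative proportions: control C = 1 − (1 − w)(1 − q); treated T = 1 − (1 − 0.7w)(1 − q); apparent reduction = 1 − T/C.
- Person-time with constant hazards: H(x) = −ln(1 − x); apparent reduction = 1 − [H(0.7w) + H(q)] / [H(w) + H(q)].

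| w | q | C | T | Cumulative | Hazard ratio | Person-time |
|---|---|---|---|---|---|---|
| 25% | 50% | 0.625 | 0.5875 | 6.0% | 0.886/0.981 = 0.903 | 9.7% |
| 25% | 70% | 0.775 | 0.7525 | 2.9% | 1.396/1.492 = 0.936 | 6.4% |
| 15% | 90% | 0.915 | 0.9105 | 0.5% | 2.414/2.465 = 0.979 | 2.1% |

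The first and last rows are the extremes of the assumed ranges.

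**Lower assumed rates.** With w = 10% and the same 30% reduction, q = 30% gives C = 1 − 0.90 × 0.70 = 0.370, T = 1 − 0.93 × 0.70 = 0.349 and an apparent reduction of 5.7%. The cumulative figure is 14.2% at q = 10%, 2.7% at q = 50% and 1.2% at q = 70%. Over w = 5–15% and true reductions of 20–50%, it is 2.1–13.0% at q = 30% and 1.0–6.5% at q = 50%. The model leaves out children with one wheeze and one other illness, who also count as recurrent.

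**The opposite pull.** Wheeze follow-up starts at D01, so an acute RSV illness seen by a GP can itself be an episode. Protocol 2.2 gives 13.9–27.4 RSV GP consultations per 100 UK children in the first year of life, depending on birth month. If nirsevimab cut these by 60% (assumed, borrowed from the hospitalization design effect in Protocol 9.2), 0.60 × 13.9 = 8.3 and 0.60 × 27.4 = 16.4. About 8–16 potentially qualifying consultations per 100 children would then disappear. Not all would meet the definition, and two episodes are needed, so this shows direction and not an effect size.

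**The case against.** A reader might infer that the endpoint mostly measures routine infections and would hide a real effect. The documents do not support that.

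- **No rates.** Neither document gives the share of qualifying episodes that are not wheeze. *Mostly* has no figure behind it.
- **An entry filter exists.** The parent question is about cough, chest and breathing, so an ear-only infection may never reach record review. This stands, but the filter is partial: a medicated cold with cough passes it.
- **The direction is not fixed.** Non-wheeze events need not be equal between arms, because acute RSV visits can qualify. Protocol 6.3.2 itself calls the direction of open-label bias uncertain.
- **The scale matters.** The SAP ends follow-up at the second episode, and Protocol 9.4.3.3 lists "Recurrent wheeze throughout the study period in UK reconsented participants" for efficacy by the exact person-time method. On that scale the dilution is smaller than cumulative proportions suggest, though still large.
- **Low decision weight.** No hypothesis is tested, and the amendment history in Protocol 10.6 presents wheeze collection as an addition to an extension set up to study antibody-dependent enhancement. This lowers the severity. It does not correct the label on the reported incidence.
- **The detail may already be recorded.** The eCRF is not among the documents, and the protocol already collects event details and medications prescribed during wheeze. If the criterion is recorded, the remedy is only a derivation.

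**Conclusion.** The point holds in a limited form. On its plain wording the definition admits illness without wheeze, the SAP carries this into recurrent wheeze, and no planned analysis isolates physician-diagnosed wheeze or asthma. The reported incidence may therefore not match its objective. A between-arm difference could be diluted, or an apparent one could arise from prevented acute RSV illness.

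The size is unknown. The ranges of 0.5–6% (cumulative) and about 2–10% (person-time) for a true 30% reduction rest wholly on the assumed w and q, on independence and, for the second range, on constant hazards. It would be wrong to conclude from them that a real effect will be missed. Severity is optional to modest, and no primary or key secondary analysis is affected.

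**What to change.** In SAP 6.6.4.3.7:

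1. Add a tabulation, by arm and for the same three periods, of participants with two or more episodes of physician-diagnosed wheeze or asthma.
2. Show it beside the broad protocol definition, labelled as wheeze or medicated ENT/respiratory illness.
3. Derive the criterion met from the event and medication details already collected in the record review, and report how many episodes cannot be classified.
4. Where dates and RSV results allow, repeat the strict row without episodes that coincide with a recorded RSV LRTI hospitalization. Acute RSV illness managed outside hospital would remain, so this removes only part of the overlap.

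While editing, reconcile Protocol 9.4.3.3, which lists recurrent wheeze for efficacy with a 95% CI, with the SAP's descriptive-only statement.

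The cost is a derivation and a few table rows if the recorded detail suffices. If it does not, the remedy should stop at reporting the unclassifiable count. SAP version 6.0 is dated 14 January 2025 and the planned last visit is 28 February 2025, so a new eCRF flag could mean abstracting records again. The strict row may miss wheeze that was not labelled as such; the broad row remains for that reason.

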8.1.3 Immunogenicity Assessments

No immunogenicity data will be obtained in the study.

8.2 Safety Assessments

This section presents safety assessments other than adverse events which are presented in Section 8.3.

Planned time points for all safety assessments are provided in the SoA (Section 1.3).

Safety data are reported by parents/LARs of participants through an eDiary. From D01 to D366, each time a health event will be captured on the eDiary, a medical call center will contact parents/LARs to collect and report the health event's information in the eCRF. The Investigator or delegate site staff will review information reported in the eCRF and interview the participants' parents/LARs if any additional information needs to be collected. Parents/LARs who don't have access to the eDiary will be requested to contact directly the investigation site to report any health event.

From D366 to D731, UK reconsented participants' parents/LARs will record in the memory aid any hospitalizations and emergency room visits that occurred. During the 18-month and 24-month phone calls, the Investigator or delegated site staff will interview parents/LARs to collect information reported in the memory aid and to assess the SAE relationship. Only the related SAE information will be collected in the eCRF.

8.2.1 Medical History

Prior to enrollment, participants will be assessed for pre-existing conditions and illnesses, both past and ongoing. Any such conditions will be documented in the source document. Significant (clinically relevant) medical history (reported as diagnosis) including conditions/illnesses for which the participant is or has been followed by a physician or conditions/illnesses that could resume during the course of the study or lead to an SAE or to a repetitive outpatient care will be collected in the eCRF.

Collected information will be coded.

8.2.2 Clinical Examination

At Visit 01, the Investigator or a designee may perform a routine clinical examination. Information will be recorded in the source document.

The weight at enrollment will be measured for all participants and recorded in both the source document and in the eCRF and in the IRT.

For participants randomized in the nirsevimab group, pre-immunization temperature will be collected by the investigator as per routine practice and reported on the source document. Temperature of infants is taken to support ruling out of active infections.

If a participant needs medical attention or is hospitalized during the study, information collected in the participant's medical record will be reviewed, recorded in the eCRF, and the medical event assessed accordingly (ie, non-serious AEs within 30 days post-dosing/randomization, MAAEs, AESIs, and SAEs up to D366 for all participants or related SAEs from D366 to D731 for UK reconsented participants).

8.2.3 Collection and Reporting of Adverse Events (AEs)

Immediate AEs

Following immunization, parents or LARs of participants enrolled in the nirsevimab group will be requested to remain on site for the 30 minutes immediate surveillance of their infant.

Remote safety follow-up

During the visit, parents or LARs of all participants will be provided access to the eDiary application. They will be instructed to log in the eDiary application and answer questions in case a health-related event occurs in their infant. Depending on the time post-dosing/randomization at which the infant's health-related event occur, the investigator or designee will contact the infant's parents or LARs to collect additional information.

Detailed guidance and information on the handling of the eDiary, the monthly electronic contacts, the follow-up phone contacts, and on the completion of the eCRF are provided in the corresponding manuals included in the investigator site file or regulatory binder.

A memory aid will be provided to UK reconsented participants' parents or LARs to collect any hospitalizations and emergency room visits occurring from D366 to D731 post-dosing/randomization. During the 18-month and 24-month phone calls, the Investigator or delegated site staff will interview parents/LARs to collect information reported in the memory aid and to assess the SAE relationship. Only the related SAE information will be collected in the eCRF.

Hospitalization

As part of the safety follow-up, participants will be monitored for hospitalization through the eDiary during the first year of the study and through the memory aid during the second year of the study (only for UK reconsented participants). Parents or LARs will have to report hospitalization through the eDiary. Alternatively, parents or LARs can also directly contact the Investigator.

Upon hospitalization of their infant, parents or LARs will be asked to present the study card to medical personnel. The participant card will:

- Indicate participation in a clinical study
- Invite medical personnel to provide contact details of the host medical facility.
- Remind medical personnel that an RSV test should be conducted in case hospitalization is related to a respiratory illness.

Hospitalization due to respiratory illness

Hospitalization, RSV LRTI hospitalization, and very severe RSV LRTI are defined in Section 8.1.2.

Hospitalizations due respiratory illness (including cases of very severe RSV LRTI) will be reported in a specific eCRF page.

8.3 Adverse Events (AEs), Serious Adverse Events, and Other Safety Reporting

The definitions of an AE, SAE, and the different categories of AEs can be found in Appendix 10.2.

When parents or LARs answer questions in the eDiary to report an health event in their infant, an investigation by the site or designee will be triggered to collect information on the AE in the eCRF.

The investigator and any designees are responsible for detecting through entries made by parents in the eDiary, documenting, and recording events that meet the definition of an AE or SAE and remain responsible for following up AEs that are serious, considered related to the study intervention or study procedures, or that caused the participant to discontinue the study (see Section 7).

The method of recording, evaluating, and assessing causality of AEs and SAEs and the procedures for completing and transmitting SAE reports are provided in Appendix 10.2.

8.3.1 Exemption to the Reporting of LRTI Hospitalizations as SAEs

In this study, LRTI hospitalizations of any cause including RSV LRTI hospitalizations constitute the studied clinical outcome of interest; that is, they are constitutive of the efficacy endpoints. As a consequence, LRTI hospitalizations of any cause, including RSV LRTI hospitalizations, occurring during the study will not be considered and reported as SAEs.

It is to be noted that, during the first year of the study, this exemption does not apply in the situation where the Investigator would consider the LRTI hospitalization to be related to the investigational product or to any LRTI hospitalization with a Fatal outcome. During the second year of the study, this exemption does not apply in the situation where the Investigator would consider the LRTI hospitalization to be related to the investigational product. In these situations, the events are to be reported as SAEs and the Investigator is required to follow the protocol-specified process for reporting SAEs to the GPV Department (See Section 10.2.4).

